2. TRIAL OBJECTIVES AND ENDPOINTS

2.1 MAIN OBJECTIVES, PRIMARY AND SECONDARY ENDPOINTS

2.1.1 Main objectives

This double-blind, placebo-controlled, randomised Phase II trial will be performed in female patients with HR+/HER2- advanced or metastatic breast cancer and non- visceral disease. The main objective of the trial is to assess the efficacy of xentuzumab in combination with everolimus and exemestane over everolimus and exemestane in this patient population. Efficacy will be assessed by determining whether or not the criterion for expanding the trial seamlessly into a Phase III trial is met. If the seamless option is met the trial will be expanded into a confirmatory Phase III trial with formal superiority hypothesis testing. If the seamless option is not met, the observed results will be evaluated in an explorative manner to see if they are sufficient for further development of this compound in this indication.

All imaging-related endpoints will be both independently assessed (in a blinded fashion) and investigator assessed according to RECIST 1.1 (see [Appendix 10.4](#)). The data from the independent assessments will be considered primary, with investigator assessment data as supportive.

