7.3 PLANNED ANALYSES

The primary analysis of PFS for this Phase II trial will take place when approximately 40 patients have had disease progression (assessed by independent review) or died. The time point of reaching 40 events will be estimated using investigator assessed events and the discrepancy rates observed between independent and investigator data during the trial. The estimation of this time point is likely to lead to some deviation, though relatively small, from the planned 40 independent assessed events. Based on assumed median PFS times (refer to [Section 7.7](#)), the analysis is expected to take place 15 months after the last patient has been randomised. This analysis will be performed by the DMC.

If the criterion for the seamless option is met then the trial will be expanded into a confirmatory Phase III trial and remain double-blind. If the criterion is not met then the database will be unblinded and a clinical trial report (CTR) written, including the evaluations of the primary, secondary and further endpoints. Note that based on these results it is still possible that clinical development in this indication will be continued (e.g. via a separate Phase III trial), in addition patients randomised into this Phase II trial will have further data collected and reported upon, beyond the unblinding time-point. Blinded dummy treatment group assignments will be used in the study database whilst the trial remains blinded. [Section 4.1.6](#) provides further details on the blinding and procedures for unblinding.

An exception to the above plan will occur if the proportion of randomised patients dropping out of the trial without evidence of disease progression, becomes so high that reaching 40 PFS events is either not possible, or has not been met 20 months after the last patient has been randomised. In such an unlikely scenario no DMC analysis will be performed and therefore

the criterion for seamless expansion will not have been met. In this situation the database will be unblinded and a CTR written, including the evaluations of the primary, secondary and further endpoints.

Imaging related endpoints will be both independently assessed and investigator assessed according to RECIST 1.1. The data from the independent assessments will be considered primary, with investigator assessment data as supportive.

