7.7 DETERMINATION OF SAMPLE SIZE

For the primary endpoint of PFS, it is assumed that xentuzumab in combination with everolimus and exemestane will increase the median from 9.9 months ([R16-0802](#)) in the everolimus and exemestane alone group to 19.8 months. Assuming an exponential distribution, this is equivalent to a reduction in the risk for progression of disease or death of 50%, corresponding to an underlying hazard ratio (HR) of 0.50. With 80 eligible patients randomised over a 15 month period, 40 PFS events are predicted to be reached on average around 30 months after the first patient is randomised. This assumes approximately 20% of patients randomised will either drop out of the trial without evidence of disease progression or be assessed as non-PD by independent assessment when the investigator assigned disease progression. If this proportion differs significantly from the 20% assumed then the number of patients randomised may be increased in order to observe 40 PFS events in a timely manner, but the number of patients randomised will not exceed 100 patients.

[Table 7.7: 1](#) shows the probability of observing various HR thresholds for different underlying (true) HR values and accrued PFS events.

Table 7.7: 1 Probability (%) of observed HR for a range of underlying HRs and PFS event numbers

PFS Events	Underlying (True) HR	Probability ¹ observing HR			
		≤0.50	≤0.60	≤0.75	>0.75
50	HR=1.00	0.7%	3.5%	15.5%	84.5%
40		1.4%	5.3%	18.1%	81.9%
30		2.9%	8.1%	21.5%	78.5%
50	HR=0.60	26.0%	50.0%	78.5%	21.5%
40		28.2%	50.0%	76.0%	24.0%
30		30.9%	50.0%	72.9%	27.1%
50	HR=0.50	50.0%	74.0%	92.4%	7.6%
40		50.0%	71.8%	90.0%	10.0%
30		50.0%	69.1%	86.7%	13.3%
50	HR=0.40	78.5%	92.4%	98.7%	1.3%
40		76.0%	90.0%	97.7%	2.3%
30		72.9%	86.7%	95.7%	4.3%

¹ Calculated using the approximate normal distribution of the estimated log HR

With 40 PFS events, if the underlying HR is 0.50, the chance of observing a treatment effect with HR of ≤0.60 is 71.8%, while the chance of observing a treatment effect with HR of ≤0.75 is 90.0%. Also, if the underlying HR is 1.0, the chance of observing a treatment effect with HR of ≤0.60 is 5.3%, while the chance of observing a treatment effect with HR of ≤0.75 is 18.1%. If the PFS events were increased from 40 to 50, the probability of observing a treatment effect with HR of ≤0.60 is increased by 2.2% (from 71.8% to 74.0%) for an underlying HR of 0.50, similarly for a treatment effect with HR of ≤0.75 the increase in probability is 2.4%.

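### Section 7.3 records the expansion criterion as not met, with no DMC look, if high dropout leaves fewer than 40 PFS events at 20 months, and at a given loss this happens far more often when xentuzumab works

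*Protocol*

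**What the plan says.** Section 7.3 sets the normal rule: "The primary analysis of PFS for this Phase II trial will take place when approximately 40 patients have had disease progression". Deaths count as well, and progression is judged by independent review. The look is expected 15 months after the last randomisation, and the DMC performs it.

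The exception is tied to heavy dropout among patients who have not progressed, without a percentage. Its trigger is that "reaching 40 PFS events is either not possible, or has not been met 20 months after the last patient has been randomised". Two consequences follow. The first is stated as "In such an unlikely scenario no DMC analysis will be performed". The second is that the expansion criterion is treated as failed. The database is then unblinded and a clinical trial report (CTR) is written covering all endpoints.

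The consequence reaches the main objective. Section 2.1.1 states: "Efficacy will be assessed by determining whether or not the criterion for expanding the trial seamlessly into a Phase III trial is met". Section 7.2 repeats this and makes the hazard ratio the quantity that decides. Section 7.7 assumes 20% loss and allows, but does not require, enlargement to at most 100 patients if loss differs significantly from that.

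**The concern.** The exception is meant to respond to dropout, but what triggers it is an event count at a calendar limit, and that count depends on the treatment effect as well as on loss. Of two trials with identical loss, the one with an ineffective drug collects events quickly, passes the gate and gets its DMC analysis. The one with an effective drug collects them slowly and is more likely to be assigned *not met* without the hazard ratio being compared with the criterion.

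At stake is the seamless option. In the high-loss setting the exception was written for, the plan can become less likely to expand the better the drug is, and an unevaluated criterion is reported as a failed one.

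**Working it through.** **Inputs.** From 7.7: control median 9.9 months, exponential PFS, design HR 0.50, 80 patients over 15 months, 20% loss, cap of 100. From 7.6: 1:1 allocation. From 7.3: limit 20 months after the last randomisation, so month 15 + 20 = 35. My assumptions: uniform accrual, the same loss in both arms, and lost patients never give a counted event.

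**Reproducing the plan's figures.** Table 7.7: 1 follows from P(observed HR ≤ c) = Φ[(ln c − ln HR)·√d/2]. At d = 40 and HR 0.50 this gives 71.8% for c = 0.60 and 90.0% for c = 0.75; at HR 1.0 it gives 5.3% and 18.1%. All match. The timing gives 40 expected events at month 27.8; the protocol's figure of about 30 months needs a back-loaded accrual that it does not state.

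**Chance of missing the gate.** With λ = ln 2/9.9, A = 15 and T = 35, an unlost patient has an event by T with probability

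p(HR) = 1 − [exp(−λ·HR·(T−A)) − exp(−λ·HR·T)]/(λ·HR·A),

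which is 0.847 at HR 1.0, 0.614 at 0.50, 0.534 at 0.40 and 0.436 at 0.30. At 30% loss with 40 patients per arm, expected events are 40 × 0.7 × (0.847 + 0.847) = 47.5 at HR 1.0, and 40 × 0.7 × (0.847 + 0.614) = 40.9 at HR 0.50. The total is the sum of two binomials, each with success probability (1 − loss)·p. P(fewer than 40 events):

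| Patients | Loss | HR 1.0 | HR 0.50 |
|---|---|---|---|
| 80 | 20% | <0.1% | 4.8% |
| 80 | 30% | 3.6% | 37.4% |
| 80 | 40% | 39.6% | 84.4% |
| 100 | 30% | 0.0% | 0.4-0.9% |
| 100 | 35% | ≤0.1% | 3-5% |
| 100 | 40% | 0.7-1.2% | 13-19% |

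Ranges for 100 patients cover accrual at the planned rate (100 × 15/80 = 18.75 months) and accrual squeezed into 15 months.

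**Sensitivity.** With back-loaded accrual and 8-weekly scans, which puts the 40th event near month 30, the 80-patient figures at HR 1.0 versus 0.50 are 0.1% versus 11.1% (20% loss) and 7.4% versus 52.1% (30% loss). With exponential dropout of the same crude size they are 0.5% versus 9.2% (30%) and 12.3% versus 42.0% (40%). The direction never changes.

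**Effect on the decision.** The real cut-off is in the DMC charter, so I use 0.60, a column of Table 7.7: 1, as an illustration. With 80 patients and 30% loss, P(met) as written is P(at least 40 events) × P(HR ≤ 0.60 at 40 events):

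- HR 0.50: 0.626 × 0.718 = 45%
- HR 0.40: 0.424 × 0.900 = 38%
- HR 0.30: 0.202 × 0.986 = 20%

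If trials with d = 30 to 39 events are also analysed, with cut-off exp[ln 0.60 × √(40/d)], these become 70%, 87% and 91%. The null pass probability is 5.3%.

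**The case against.** **Only the seamless route is lost.** A reader might infer that usable data are discarded and that the decision on the drug itself is biased. The documents do not support that. In the exception 7.3 still evaluates all endpoints in the CTR, the SAP (sections 3 and 7.4.1) estimates the stratified hazard ratio for the non-expanded trial, and 2.1.1 and 7.2 leave a separate Phase III open. This stands and limits the consequence.

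**The plan has its own safeguard.** At the planned 20% loss the risk at HR 0.50 is about 5%, so calling the scenario unlikely is fair there. Enlargement to 100 removes most of the risk up to about 35% loss. This stands too, but enlargement is optional, and the exception has to work when loss is high: the rationale in Global Amendment 4 already cites more early dropout than expected.

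**The target is only approximate.** Section 7.3 allows a small deviation from 40. The exception sentence itself says 40, and even if 38 counted, 22% of trials at HR 0.50 would be stopped against 1% at HR 1.0 (80 patients, 30% loss).

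**High loss may be informative.** Patients who leave with symptomatic progression or adverse events and start new therapy are censored (Table 7.5: 1), so the hazard ratio may be biased as well as imprecise. That is a fair caution about expanding. It does not justify this gate, because the same loss with 40 events still gets its DMC analysis.

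**Thirty events are not as good as 40.** Table 7.7: 1 gives 69.1% at 30 events against 71.8% at 40 (HR 0.50, cut-off 0.60), and a reader might infer that little is lost. With that fixed cut-off the null pass rate rises from 5.3% to 8.1%. With the cut-off rescaled to 0.554, the chance of passing at 30 events is 61%.

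**Conclusion.** The concern holds for the seamless option. At a given loss the 40-event gate is missed far more often when xentuzumab works: 4% versus 37% at HR 1.0 and 0.50 with 80 patients and 30% loss. In that setting the chance of meeting an illustrative 0.60 cut-off falls as the drug improves. The size depends heavily on loss and on whether the trial is enlarged.

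A reader might also infer that efficacy alone can trigger the exception. It cannot in practice: with no loss, 40 events are essentially always reached by the limit at HR 1.0 and 0.50. At 40% loss or more with 80 patients, ineffective drugs are often stopped as well.

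The figures rest on exponential PFS, uniform accrual, equal loss by arm, an unbiased hazard ratio and an illustrative cut-off. Sections 1.4 and 4.1.6.1 report that the Phase II primary analysis has been done and showed no added benefit, so the point now matters for the design record and for any reuse of the rule. It should be corrected there, but it does not undermine the reported result.

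**What to change.** Replace the cancellation in 7.3. At 20 months after the last randomisation, the DMC performs the planned analysis on the independently assessed events available, provided there are at least 30, the smallest event number in Table 7.7: 1. The charter rescales its cut-off for d events (log cut-off × √(40/d)) so that the null pass probability equals that at 40. The DMC sees dropout by arm and reason alongside the hazard ratio, because the loss may be informative. With fewer than 30 events, record the criterion as *not assessed*.

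Consequential checks: recompute the 0.0028 probability in 7.4 and confirm the information fraction, which 7.4 already plans to update. Restate the 40 + 136 split in 7.7 as d + (176 − d), so the total stays 176.

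Cost: a few sentences in 7.3, 7.4, 7.7 and the charter, and no extra Phase II patients or time. The downside is precision: the standard error of the log hazard ratio is 2/√30 = 0.37 at the floor against 2/√40 = 0.32. With the rescaled 0.60 cut-off at HR 0.50, the chance of passing is 61% at 30 events and 69% at 37, against 72% at 40. Fewer than 30 events would be rare at HR 0.50 (about 0.5% with 80 patients and 30% loss).

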7.3.1 Primary endpoint analyses

The primary endpoint of this study is PFS defined as the time from the date of randomisation to the date of disease progression, or to the date of death if a patient died earlier. The date of progression will be based on independent assessment according to the RECIST 1.1 criteria.

For patients with ‘event’ as an outcome for PFS:

- PFS [days] = date of outcome – date of randomisation + 1

For patients with ‘censored’ as an outcome for PFS:

- PFS (censored) [days] = date of outcome – date of randomisation + 1

The censoring rules for PFS (i.e. outcome and date of outcome) are described in [Table 7.5: 1](#). The time frame for the primary assessment of PFS will be from randomisation until the earliest of disease progression, death or the time point of the primary PFS analysis (refer to [Section 7.3](#)).

A stratified log-rank test will be used to test the primary hypotheses, if the trial is expanded into a Phase III trial.

A stratified Cox proportional hazards model will be used to estimate the hazard ratio and its asymptotic two-sided 95% Wald CI between the two treatment groups. A hazard ratio of less than one will favour the xentuzumab in combination with everolimus and exemestane treatment group.

Kaplan-Meier (KM) estimates will be used to display the distribution of PFS for each treatment group on a KM curve. To support the plot estimated survival probabilities at specific time points of interest (scheduled imaging time-points) will be tabulated along with 95% confidence intervals, using Greenwood’s variance estimate. In addition the survival distribution will be used to provide estimates of the median, 25th and 75th

percentiles.

7.3.2 Secondary endpoint analyses Overall survival

OS will be analysed using the same statistical methods as for PFS. OS will be included in the confirmatory strategy in a hierarchical manner if the trial is expanded into a Phase III trial.

OS is defined as the time from randomisation until death from any cause. For patients with ‘event’ as an outcome for OS:

- OS [days] = date of outcome – date of randomisation + 1.

For patients with ‘censored’ as an outcome for OS:

- OS (censored) [days] = date of outcome – date of randomisation + 1

The censoring rules for OS (i.e. outcome and date of outcome) are given in [Table 7.5: 2](#). The time frame for the primary assessment of OS will be from randomisation until the earliest of death or the time point of the primary OS analysis (refer to [Section 7.3](#)).

In addition to the main analysis the following analyses may be performed to examine the pattern of time to death for consistency with the PFS results, while accounting for the extent and influence of post-progression intervention if deemed necessary:

- describe the cumulative proportion of deaths at each scheduled tumour assessment time point
- tabulate the specific anti-cancer treatments after progression
- describe the effect of additional anti-cancer treatment, by separating patients into the following sub-groups:
 - those not eligible for additional treatment
 - patients who did not progress

- patients who died within one month of progression
- those eligible for additional treatment (i.e. those who have progressed and not died in the first month after progression)
 - did not take additional treatment
 - did take additional treatment

Disease control

DC will be analysed in terms of DC rate (DCR), defined as the proportion of patients with best overall response of CR, PR, SD or Non-CR/Non-PD. The DCR will be calculated for each treatment group, overall and within each level of the stratification factors. Proportions will be presented with 95% CIs. A logistic regression model adjusting for the stratification factors where appropriate will be used to compare the DCR between the two treatment groups.

For the primary assessment of DC, tumour imaging will be performed every 8 weeks up to week 80 and every 12 weeks thereafter until the earliest of disease progression, death or last evaluable tumour assessment before the start of subsequent anti-cancer therapy or the time point of the primary PFS analysis (refer to [Section 7.3](#)).

A best overall response of SD or Non-CR/Non-PD must have a minimum duration of 24 weeks from the date of randomisation.

Duration of disease control

For all patients with DC the duration of DC is defined as the time from randomisation until the earliest of disease progression or death.

For patients with disease progression or death:

- Duration of DC [days] = date of outcome – date of randomisation + 1

For patients without disease progression or death:

- Duration of DC (censored) [days] = date of outcome – date of randomisation + 1

The censoring rules for DC (i.e. outcome and date of outcome) are described in [Table 7.5: 1](#). The time frame for the primary assessment of duration of DC will be from randomisation until the earliest of disease progression, death or the time point of the primary PFS analysis (refer to [Section 7.3](#)).

Kaplan-Meier estimates will be used to calculate median duration of DC for each treatment group.

Objective response

OR will be analysed in terms of OR rate (ORR), defined as the proportion of patients with best overall response of CR or PR. The ORR will be calculated for each treatment group, overall and within each level of the stratification factors. Proportions will be presented with 95% CIs. A logistic regression model adjusting for the stratification factors where appropriate will be used to compare the ORR between the two treatment groups.

For the primary assessment of OR, tumour imaging will be performed every 8 weeks up to week 80 and every 12 weeks thereafter until the earliest of disease progression, death or last evaluable tumour assessment before the start of subsequent anti-cancer therapy or the time point of the primary PFS analysis (refer to [Section 7.3](#)).

As per RECIST 1.1 guidance confirmation of OR is not a requirement for randomised trials.

Time to pain progression or intensification of pain palliation

Xentuzumab may delay the time to pain worsening. To investigate this, each patient's pain severity and usage of pain palliation will be assessed. Time to pain progression or intensification of pain palliation is defined as the time from randomisation until the earliest of a clinically significant increase in pain (≥ 2 -point increase from baseline in the BPI-SF Item 3) without a decrease in analgesic use, intensification in pain palliation (≥ 2 -point increase in the 8-point AQA) or death.

For patients with 'event' as an outcome for pain progression/intensification of pain palliation:

[figure not shown]
- Progression/intensification [days] = date of outcome – date of randomisation + 1.

[figure not shown]
For patients with 'censored' as an outcome for pain progression/intensification of pain palliation:

[figure not shown]
- Progression/intensification (censored) [days]=date of outcome – date of randomisation + 1

The censoring rules for time to progression/intensification (i.e. outcome and date of outcome) will be described in the TSAP. Time to progression/intensification will be analysed using the same statistical methods as for the primary endpoint.

The time frame for the primary assessment will be from randomisation until the earliest of pain progression, intensification of pain palliation, death or the time point of the primary PFS analysis (refer to [Section 7.3](#)).

7.3.4 Safety analyses

Adverse events will be coded using the Medical Dictionary for Drug Regulatory Activities (MedDRA). Standard BI summary tables and listings will be produced. All adverse events with an onset between start of treatment and end of the REP, a period of 42 days after the last dose of trial medication, will be assigned to the on-treatment period for evaluation. As the treatment arms are made up of a combination of individual treatments a patient may have multiple last doses of treatment; therefore the last dose of study medication is defined as the latest of these.

All treated patients will be included in the safety analysis, according to the actual trial medication they received. In general, safety analyses will be descriptive in nature and will be based on BI standards. No hypothesis testing is planned.

Statistical analysis and reporting of adverse events will concentrate on treatment-emergent adverse events, i.e. all adverse events occurring between start of treatment and end of the residual effect period. Adverse events that start before first drug intake and deteriorate under treatment will also be considered as ‘treatment-emergent’.

Frequency, severity, and causal relationship of adverse events will be tabulated by system organ class and preferred term after coding according to the current version of the MedDRA at the database lock.

Laboratory data will be analysed both quantitatively as well as qualitatively. The latter will be done via comparison of laboratory data to their reference ranges. Values outside the reference range as well as values defined as clinically relevant will be summarised. Treatment groups will be compared descriptively with regard to distribution parameters as well as with regard to frequency and percentage of patients with abnormal values or clinically relevant abnormal values.

Vital signs, physical examinations, or other safety-relevant data observed at screening, baseline, during the course of the trial and at the end-of-trial evaluation will be assessed with regard to possible changes compared to findings before start of treatment.

